## Kranus Health GmbH\_DINKS

Multiplicity: The primary endpoint (1) and the first 3 secondary endpoints (2) - (4) are tested sequentially according to the method of a priori ordered hypotheses: The primary endpoint (1) relative change rel-CfB-IEF week 12 with respect to baseline of incontinence episodes is analysed using an analysis of covariance with the factor treatment group and the baseline value of the IEF as covariate; the significance level is 5% 2-sided. If significance is reached for endpoint (1), endpoint 2 (change in the ICIQ-SF questionnaire) is tested analogue to the 5% 2-sided level. If significance is reached for endpoint (2), endpoint (3) (change in quality of life in the I-QOL questionnaire) is tested 2-sided analogue to the 5% level. If significance is reached for endpoint 3, endpoint 4 (PAM-13) is tested 2-sided analogue to the 5% level. The other endpoints are analysed descriptively with p-values and 95% CIs. The FAS (ITT) is the primary evaluation collective for efficacy; missing values for the main outcome variables (1) - (4) are imputed using the JtR method.

## Subgroup analyses:

Descriptive subgroup analyses are performed for the primary and secondary efficacy variables using the ICD code:

- N39.3 Stress incontinence [stress incontinence]
- N39.42 Urge incontinence
- Mixed incontinence - both codes

and using the S/U-IQ (Stress/Urge Incontinence Questionnaire and Classification System) for the indications:

- pure stress urinary incontinence ( $SUI \geq 4$ ,  $UUI=0$ ),
- Mixed urinary incontinence, predominantly stress component ( $SUI > 0$ ,  $SUI > UUI$ ;  $UUI > 0$ ),
- balanced mixed urinary incontinence ( $SUI > 0$ ,  $SUI=UUI$ ),
- Mixed urinary incontinence, predominantly urge component ( $SUI > 0$ ,  $UUI > 0$ ,  $UUI > SUI$ )
- Pure urge incontinence ( $UUI \geq 4$ ,  $SUI =0$ )

carried out.

Further subgroup analyses are carried out:

- Medication for the treatment of incontinence (yes/no),
- Premenopausal/menopausal/postmenopausal status,
- Age categories < 45, 45-60, > 60 years,
- BMI,
- Country of birth,
- Level of education,
- Secondary diseases,
- Smoking behaviour,
- Alcohol consumption,
- Number of births,

## Kranus Health GmbH\_DINKS

- Type of delivery,
- Time since last delivery
- Duration of illness,
- Pre-existing pelvic floor course,
- Non-bladder-specific medication,
- Frequency of use of the app.

The I-QOL and ICIQ are also analysed individually.

The results of the subgroup analyses are also graphically presented and summarised using forest plots.

Evaluation collectives:

- Full Analysis Set (FAS) contains all patients who were randomised. Patients who withdrew their consent immediately after randomisation are not included in this data set.
- Per-Protocol Set (PPS) contains all FAS patients from whom no significant study protocol violations were reported.
- Complete cases (CCS): Patients with complete data per evaluation.
- Safety Set (SAF) contains all patients who are included in the study (signed informed consent form). It is expected that SAF and FAS are identical.

Sensitivity analyses are carried out:

1. CCS analysis
2. FAS analysis with last-observation-carried-forward-option (LOCF).

## 8.9 Presentation of the results

The results are presented in close accordance with the guideline "Structure and Content of Clinical Study

Reports E3" (ICH-E3) are presented in tabular form (Section 8.10) and as listings (Section 8.11).

### 8.10 Tables

- Demographic data and other baseline characteristics
- Primary endpoint
- Secondary endpoints

### 8.11 Listings

- List of dropouts who have withdrawn their declaration of consent (WoC)
- Curriculum deviations - (NtF)

## Kranus Health GmbH\_DINKS

- Patients for whom deviations from the study plan lead to exclusion from the PPS (drop-outs)
- Demographic data (height, age, weight, etc.)
- Other baseline characteristics
- Individual data and results for primary and secondary endpoints
- Adverse events (AE/SAE and events)

### 8.12 Data collection/documentation forms

In order to achieve the study objective, it is necessary to collect and process medical data from individual patients. Data is collected using electronic questionnaires, which are completed by the patients at the beginning (baseline) and at the end of the study (PROM).

The data to be analysed from the patients is collected in the app on the one hand and via an ePRO system on the other, and the latter is stored in an eCRF. The questionnaires, which are to be completed independently at the beginning (baseline/V1) and at the end of the study (V3), are collected via an ePRO system and stored in the EvidentIQ software. Further technical parameters are listed in the separate document "Confirmation of validation of EvidentIQ Germany's Marvin software and secure data hosting".

A detailed statistical analysis plan (SAP) is created before the evaluation.

Kranus Health GmbH\_DINKS

## 9 Data management

### 9.1 Patient identification

All patient-related data is collected by Kranus Health GmbH in pseudonymised form. For this purpose, a non-verbal pseudonym is used, from which alone the identity of the patient cannot be deduced. The patient identification number is assigned centrally as part of the internet-based registration process.

After registration of the patient and scheduling of the informed consent discussion, the trial centre receives an e-mail with the patient identification number and the information that a new registration and scheduling has been received. This e-mail, together with the information provided by the patient during registration, is used by the trial centre to carry out the patient information on behalf of the sponsor and to have the patient information provided by Kranus signed to obtain consent for participation in the trial. Once consent has been obtained, it will be together with the patient identification list for the sponsor for 10 years in accordance with the requirements of the MDR.

### 9.2 Data acquisition

Electronic data recording is carried out via EvidentIQ's eCRF on a proprietary server. Information on data security and compliance of the server structure is specified in the appendix.

### 9.3 Data protection

As part of the study, it is necessary to collect and process personal data from the study participants (e.g. full name, initials of first name and surname, date of birth, address) and data on treatment and the course of the disease (e.g. medical findings, types of treatment, prescribed medication). This data is generated by the patients themselves and stored electronically on the study server in pseudonymised form (i.e. without direct reference to the patient's name) with the help of a patient identification number, transmitted to the responsible data processing body and evaluated.

The trial participants will be informed about the disclosure of their pseudonymised data to the recipients named therein as part of the documentation and notification obligations. Persons who do not consent to the disclosure will not be included in the clinical trial.

If patients withdraw their consent to the study, including further data collection, no further data will be collected from the time of withdrawal. The data collected to date will continue to be used and analysed within the study, but can be deleted at the patient's request during the study period. If a patient only cancels the study treatment, the data required for the study can continue to be collected and used as long as the patient has not withdrawn their consent.

### 9.4 Quality assurance

Only PROMs are collected in the study; monitoring is not planned.

Kranus Health GmbH\_DINKS

## 9.5 Archiving

All documentation forms, consent forms and other important trial documents are stored for at least 10 years in accordance with Section 13 (10) GCP-V. The patient identification list is kept separately from the documentation records in all centres.

Kranus Health GmbH\_DINKS

## 10 Ethical issues, legal and administrative regulations

### 10.1 Declaration of Helsinki and Good Clinical Practice

The study is conducted in accordance with the ethical principles that have their origin in the Declaration of Helsinki [39]. The current version of the Declaration will be observed.

The recommendations of Good Clinical Practice [39], valid since 17 January 1997, are taken into account where applicable.

### 10.2 Independent ethics committees

The study protocol is submitted with the necessary additional documents to the responsible ethics committee of the scientific director with a request for evaluation. The study can only begin after the ethics committee has given its approval.

### 10.3 Legal regulations

The Kranus Mictera app is an approved Class I medical device.

### 10.4 Registration

The study should be entered in the following public register: German Clinical Trials Register (DKRS, <https://www.drks.de>).

### 10.5 Financing

The study is financed by Kranus Health GmbH.

### 10.6 Final report and publication

The final report will be completed by 15 April 2025. Publication will be primarily in a peer-reviewed journal. The order of authors will be determined by the scientific director in collaboration with the sponsor. The results of the study will be published regardless of the outcome.

## A. Appendix

### A1. Questionnaires used

#### A1.1 PGI-I: Patient Global Impressions Scale - Improvement

Please select the number that best reflects the condition of your incontinence now in the compared to before the therapy:	
Much better	1
Much better	2
A little better	3
unchanged	4
A little worse	5
Much worse	6
Much worse	7

Kranus Health GmbH\_DINKS

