
Target values/criteria/endpoints:
	
Primary endpoint:
 
(1) Relative change (rel-CfB-IEF) in IEF from baseline to week 12 relative to baseline; desired reduction in mean relative IEF by 50% [6] [7]; IEF per 24 hours - averaged over 72 hours
 
Secondary targets / secondary target criteria:
 
(2) Change (CfB) in the ICIQ-SF from baseline to week 12; expected mean difference between the groups of <math>\geq 2.9</math> points [8, 9]
 
(3) Change in I-QOL from baseline to week 12; expected mean difference between the groups of <math>\geq 6.3</math> points [9]
 
(4) Change in the PAM-13 questionnaire from baseline to week 12
 
(5) PGI-I questionnaire (overall improvement after treatment) at week 12
 
(6) Share of the patients without incontinence (cured patients) at the end of the study
 
(7) Change in micturition frequency per day from baseline to week 12
 
(8) Change in micturition frequency at night from baseline to week 12
 
(9) Change in pad consumption from baseline to week 12
 
(10) Change in imperative urge to urinate from baseline to week 12
 
(11) Change in functional bladder capacity from baseline to week 12
 
(12) Change in body weight from baseline to week 12
 
(13) Proportion of patients with treatment failure within the study period
 
(14) Proportion of patients with at least 50% reduction in IEF from baseline to week 12
 
(15) Change in stress incontinence episodes of the S/U-IQ from baseline to week 12
 
(16) Change in urge incontinence episodes of the S/U-IQ from Baseline at week 12

--	---

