## Kranus Health GmbH\_DINKS

- Newly started drug or physical therapy for micturition symptoms (anticholinergics, beta-3 receptor agonists, phytopharmaceuticals, biofeedback, EMS) in the last 4 weeks
- Severe psychiatric disorders that make it impossible to use the app
- Neurological diseases that affect the urinary tract
- Tumour and incontinence operations in the small pelvis
- Obesity per magna (BMI >35)
- Recurrent urinary tract infections N39.0 (at least 2 within 6 months or 3 infections within one year)
- Participation of the patient in another clinical trial within the last 4 weeks prior to inclusion
- addiction or other illnesses that do not allow the person concerned to assess the nature, scope and possible consequences of the clinical trial

Both groups, intervention and control group, have access to the treatment options of the regular care reality during the study period. In order to be able to evaluate the effect of the intervention in a differentiated manner, ongoing incontinence treatment (e.g. medication, interventional or surgical measures) should have been started at least four weeks before the start of the study. New therapies before the start of the study are considered an exclusion criterion.

During the study period, all newly initiated therapies for incontinence treatment (e.g. medication, interventional or surgical measures) are recorded and categorised as treatment failure. Treatment failure is also deemed to have occurred if the patient reports a deterioration in the PGI-I questionnaire at the end of the study.

The number of treatment failures is calculated and documented separately for the intervention and control groups.

Patients in the control group are not given access to the app-based intervention during the twelve-week study period. After completion of the survey at the end of the study (week 12, see 1.5. Visit schedule), they are free to use the app-based therapy.

Kranus Health GmbH\_DINKS

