### 5.2.6 Further questions about app use

In week 12, the intervention group receives the following additional questions, which the patient can answer voluntarily:

- Please select the number that best describes the condition of your incontinence now compared to before the therapy: A scale of 1-7 (1 much better - 7 much worse) is provided here.
- How often have you accessed Mictera? (Several times a week, weekly, with longer breaks than 1 week, with longer breaks of between 2-6 weeks, with longer breaks of over 6 weeks, I have not used Mictera)
- If you took longer breaks or did not train with Mictera, what was the reason for this? (free text)
- How are you to recommend Kranus Mictera to others? Answer on a scale of 1-10 (1 Not at all - 10 Very much)
- How satisfied are you with the app? Answer on a scale of 1-10 (1 Not at all - 10 Very much)
- Do you have any comments or suggestions for us? The answer is given here in free text.

The control group is only asked one further question in week 12:

- Do you have any comments for us? This question can be answered in a free text field.

Both groups are asked questions in week 1:

- Please your year of birth.
- Please enter your current weight. (in kg)
- How tall are you? (in cm)

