## 5.3 Therapy failure

Treatment failure is defined as any reported worsening in the PGI-I questionnaire at the end of the study or the start of any interventions against the incontinence symptoms (conservative and invasive methods).

Kranus Health GmbH\_DINKS

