### 8.8 Statistical analysis

In general, continuous data is summarised using descriptive statistics, i.e. with the number of observations, mean, standard deviation, minimum, median and maximum. For some variables such as the primary endpoints, the change from baseline to the end of the study (change from baseline, CfB) is also output and summarised as "post-baseline". Where appropriate, 95% confidence intervals are also calculated and reported.

Categorical data is summarised using absolute and relative frequency.

The hypotheses for analysing the mean group differences in the primary endpoint are:

$$H_0: \text{rel-CfB arm A} = \text{rel-CfB arm B}$$

versus

$$H_1: \text{rel-CfB Arm A} \neq \text{rel-CfB Arm B}$$

This is analysed using an analysis of covariance with the factor treatment group and the covariate baseline. As a sensitivity analysis, the relevant changes are analysed using 2-sample Wilcoxon tests.

The continuous target variables are analysed analogously with the CfBs. The results of these analyses are presented graphically using progression curves (mean values and LS mean changes) of the original mean values and the CfBs. Ordinal endpoints (e.g. PGI) are compared between the groups using 2-sample Wilcoxon tests.

Binary endpoints (rates) are compared using Fisher tests; in addition, 95% CIs are provided for comparison between groups.

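### The PGI-I asks both arms to compare with the time before therapy, but waiting-list controls have had no study therapy at week 12, so the reference point for endpoint (5) and part of endpoint (13) is unclear

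*Combined protocol and SAP*

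**What the plan says.** Appendix A1.1 prints one PGI-I item, scored 1 to 7 with 4 as unchanged. It asks for the "condition of your incontinence now in the compared to before the therapy". No separate wording for controls appears anywhere.

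The item feeds two secondary endpoints listed in section 1.4: "5) PGI-I questionnaire (overall improvement after treatment) at week 12" and "13) Proportion of patients with treatment failure within the study period". The second depends on it through section 5.3: "Treatment failure is defined as any reported worsening in the PGI-I questionnaire at the end of the study or the start of any interventions". Section 3.2 says the same: "Treatment failure is also deemed to have occurred if the patient reports a deterioration in the PGI-I questionnaire at the end of the study".

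Both endpoints are compared between arms. Section 8.8 states: "Ordinal endpoints (e.g. PGI) are compared between the groups using 2-sample Wilcoxon tests". Binary endpoints such as (13) go to Fisher tests. Table 1 places the PGI-I at V3 (week 12) for everyone, although it marks technical-support cells as intervention group only.

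Sections 3.2 and 8.1 make clear that controls have no app access until after the week-12 survey. Both arms keep usual care, and ongoing incontinence treatment is allowed if it started at least four weeks before the study.

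Section 5.2.6 gives the intervention group a set of voluntary week-12 questions. The first is: "Please select the number that best describes the condition of your incontinence now compared to before the therapy", again on a 1 to 7 scale. It then says: "The control group is only asked one further question in week 12". That question is a free-text comment.

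**The concern.** A global impression of change has meaning only against a stated starting point. For a woman in arm A, the natural reading of the therapy is the app, which she began about 12 weeks earlier. A control has had no study therapy when she answers. If she takes a long-standing incontinence drug, she may compare with the time before that drug. If she has no treatment, the wording gives her no starting point, and she must supply one.

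A between-arm difference in (5), or in the PGI-I part of (13), could then arise partly from how the question is read and not from what the app did. This matters because superiority on the PGI-I is a listed secondary objective, and both endpoints will be reported with p-values and confidence intervals.

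The near-identical item in 5.2.6 adds a smaller question of data source. App-arm women may answer almost the same item twice, once voluntarily, and no rule says which answer is analysed.

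**Working it through.** The plan gives no expected rate, standard deviation or power for (5) or (13), so there is no planned figure to reproduce. The check is textual, followed by an illustration on assumed inputs.

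**1. Who answers.** Table 1 has no arm restriction on the PGI-I row, section 5.2.4 has none, and section 8.8 compares the groups. Both arms are meant to answer.

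**2. What the therapy can refer to at week 12.**
- Arm A, no background treatment: the app, so about 12 weeks back.
- Arm A, on background treatment: the app most naturally, but the earlier treatment is possible.
- Arm B, on background treatment: the earlier treatment, which began at least four weeks before the study, or the start of the study if she infers it.
- Arm B, no treatment: nothing in the wording; she may infer the start of the study.

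The plan expects treated women. Section 8.8 lists subgroups by incontinence medication (yes/no) and by an earlier pelvic floor course. It does not give their share.

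**3. Effect on scoring.** Take a control who worsened over the 12 weeks but is still better than before an older treatment. Read against the start of the study, she scores 5 to 7 and is a treatment failure. Read against the time before the older treatment, she scores 1 to 3, counts as improved, and is not a failure by the PGI-I route. The same state gives opposite results.

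**4. Which part of (13) is exposed.** Section 5.3 has two routes: PGI-I worsening, or the start of a new intervention. Only the first uses the anchor.

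**5. Illustration (assumed shifts, no true effect, 99 per arm from section 6.1, two-sided 5%).**

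For (13), the chance of a nominal Fisher p ≤ 0.05 is the sum over i and j of Bin(i; 99, p1) × Bin(j; 99, p2), taken over tables where Fisher p ≤ 0.05:
- 10% v 10%: 2.8%
- 10% v 15%: about 14%
- 10% v 20%: about 44%
- 10% v 25%: about 76%

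For (5), by normal approximation with a shift of d standard deviations, the chance is about Φ(d × √(99/2) − 1.96):
- d = 0.2: Φ(1.41 − 1.96) = about 29%
- d = 0.3: Φ(2.11 − 1.96) = about 56%
- d = 0.4: Φ(2.81 − 1.96) = about 80%

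These show what an anchor-only shift of a given size would do. They are not evidence that such a shift occurs.

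**6. Section 5.2.6 beside Table 1.** The section concerns additional questions that come on top of the standard instruments in 5.2.1 to 5.2.5. Controls therefore still receive the PGI-I. What stays open is whether app-arm women see the item twice, and which answer feeds (5) and (13).

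**The case against.** **The anchor may be clear enough in practice.** The item sits in an end-of-study survey, answered by women who were informed about the study and completed a baseline survey. Many controls may read it as the change since the study began. This stands as a limit: the documents do not show how controls read the item, and a reader who infers that all 99 controls lack a reference point goes beyond them. It does not remove the problem, because no text tells them to read it that way.

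**The arms are not cleanly split.** Arm A also keeps usual care, so a treated woman there could misread the item too. This stands. The ambiguity is likely greater in controls but is not confined to them, and it is too strong to say that the arms answer different questions.

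**Section 5.2.6 might seem to withhold the PGI-I from controls.** A reader might infer this from the contrast between the two question lists. The word further, the heading of the section, Table 1 and section 8.8 all point the other way. The duplicate does not by itself make the arms unequal.

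**The printed text is a translation, and a detailed SAP is promised in section 8.12.** The German screen is not visible, and the A1.1 sentence is garbled. But the same anchor appears in clean form in 5.2.6. A later SAP could name the source item, but it could not change the reference point of answers already given.

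**The endpoints are descriptive.** This stands and limits the consequence.

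**Conclusion.** The point holds as a wording defect with a limited reach. As written, the plan gives endpoint (5) and the PGI-I route to (13) no stated common reference period. It affects two of 16 endpoints, and only one of the two routes in (13).

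The size and direction cannot be derived from the documents. A comparison with the time before an older treatment could make controls look better, while answering unchanged for want of a reference point would hide change either way. A reader might infer that the PGI-I is biased in favour of the app; nothing in the plan supports a direction. A reader might also infer that the trial's main conclusion is at risk. It is not, because section 8.8 keeps (5) and (13) outside the ordered tests (1) to (4).

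The conclusion assumes that the administered item matches the printed anchor and that no instruction to participants outside these documents defines it. The source question raised by 5.2.6 is separate and needs reconciling with Table 1 and section 5.2.4.

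**What to change.** 1. In Appendix A1.1, give both arms the same reference at V3: *compared with the start of the study (your first survey, 12 weeks ago)*. Alternatively, keep the validated stem and add an instruction that defines the reference in this way.
2. In section 5.2.4 and Table 1, state that this one item is presented to both arms at V3 and is the only source for (5) and for the PGI-I part of (13).
3. In section 5.2.6, delete the near-identical voluntary item, or state that it is not used for these endpoints.
4. If data were already collected with the printed stem, report that the reference period was not defined for controls, and also show (13) without its PGI-I component.

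The cost is one changed line or one added instruction in the electronic form, and one question deleted or disclaimed. The downside is a slight departure from, or an addition to, the wording of a validated instrument; the instruction option keeps the stem itself intact.
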